In Spain, prevention and screening of HCV infection is ensured mainly through primary health care. Infection is diagnosed using serological tests followed by retests to confirm active infection. The tests are used to detect HCV RNA in blood and are carried out at specialist health centers. However, a large number of people at high risk of infection do not visit health centers regularly, and even when they do, the centers lose track of a very high percentage of patients in the follow-up stage. Thus, a simple screening method or an alternative diagnostic test that can be used in situ could make testing more widely accepted and improve rates of diagnosis, referral, and treatment.

There are several quick, highly specific, highly sensitive tests on the market for detecting HCV antibodies. The tests are fast, simple, and provide results on site. However, the need for further testing to confirm results usually involves a number of visits for testing and collection of results. Consequently, many patients are lost during follow-up. Screening strategies should therefore be capable of ensuring that active infection is correctly diagnosed. Changes in the screening algorithm have recently been proposed so that HCV-RNA can be detected directly, especially in relatively inaccessible high-risk populations such as PWID.

Here, we seek to validate and implement an alternative method to screen for HCV and other viruses in an attempt to facilitate diagnosis of HCV infection, increase referrals to specialist health centers, and thus increase treatment coverage in our area. The alternative screening method proposed requires five drops of capillary blood to be collected by finger pricking onto Whatman cards. This method is more widely accepted than venous extraction and has enabled diagnosis rates to be improved by two- to six-fold among PWID at community services in the United Kingdom.

Several studies have shown the validity of dried blood samples for detecting HCV RNA using amplification techniques. Moreover, dried blood samples can also be used to perform HCV genotyping and phylogenetic studies, which can reveal transmission networks. However, although using dried blood samples offers advantages in terms of diagnosing active infection, it does not preclude the need to call individuals back in order to give them the results and provide them with suitable advice, as samples are sent to the laboratory and the results may take some time to come through.

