Participants will be given an information leaflet and a specific informed consent form. Samples will be processed according to the study protocol (Annex 1). Clinical and epidemiological data will be recorded in a database that can be accessed by researchers from the HUIL and the CNM-ISCIH. The variables shown in section 2.4 will be recorded. This file has been included in the Register of Data Files of the ISCIH.

ELISA: A disc with a sample of dried blood will be placed in a microtube containing 300 μl of 0.5% buffer solution (PBS/BSA) and processed at $4-8^{\circ}\text{C}$ for 18-24 hours. After incubation, elutes from the dried blood samples will be tested for the presence of antibodies against HCV, HIV, and HDV, as well as for HBV surface antigen (HBsAg). Negative samples will not undergo further testing and will be considered non-infected. Positive samples will be tested using real-time PCR to confirm the positive results.

Real-time PCR: Nucleic acids will be extracted using the DSP virus pathogen kit (QIAGEN, Hilden, Germany). The samples will be stored at -80°C until use. A specific HCV test will be performed to confirm active HCV infection (HCV-RNA positive) on a Rotor Gene Q unit (QIAGEN).

PHASE II: SCREENING AT CAÑADA REAL GALIANA

Screening for HCV and the other viruses (HIV, HBV, and HDV) covered by this project will take place at Cañada Real Galiana. Screening will be conducted by nursing personnel hired specifically for that purpose. An active search will be made for

individuals who come into the shantytown from outside, and the detection test will be offered to everyone regardless of whether or not their serological condition is already known. Selection of individuals for screening will be random and consecutive.

Nursing personnel will generally be accompanied by an educator from the HRU. PWID will be offered information on prevention and the importance of early diagnosis and referral to health centers.

Information will then be provided on the goals of the study, and persons who agree to take part will be required to sign an informed consent form, provide contact data for subsequent location, and provide basic social and demographic data and information on their consumption habits. Regardless of whether or not individuals agree to take part in the study, they will all be given a card containing basic information on prevention and contact data for the internal medicine department of HUIL and the HRU.

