Data will be recorded on social and demographic details, the consumption habits of each PWID, and the acceptability of the screening test. All data will be recoded in the database by the nurse or the educator using a mobile device with Internet capability and REDCap software. Informed consent forms will be kept in the files of the researcher at the HRU office.

The Whatman™ cards will be stored in a portable refrigerator after processing (see below) and shipped via courier to the National Microbiology Center (CNM) for analysis.

If a test result is positive, the patient will be contacted and offered referral to a specialist health care center in accordance with the study algorithm to confirm the result and assess whether monitoring should begin. All subjects included in the study may contact the medical department or the Harm Reduction Unit directly to make an appointment and collect the results of their tests.

PHASE III: EFFECTIVENESS OF THE INTERVENTION

Evaluation of the effectiveness of the intervention. Drug users who test positive will be contacted and offered the possibility of referral to a specialist health care center, where access to standard confirmation tests used in hospital and access to treatment will be offered. As specified in the consent form, if a patient with a positive result cannot be contacted, regional registries and hospital patient data will be used to find the patient.

Once the patient has been found or contacted, referral to HUIL will be offered to him. The harm reduction team accompanies the drug user to hospital to be evaluated by a practitioner with expertise in assessment of liver disease severity and HCV treatment. In the first visit to the hospital, a part from the medical history and physical examination, a blood test and a Fibroscan® will be performed. These blood tests will confirm the results from the screening for HCV in Cañada Real.

At this point, all PWID will be offered substitution therapy with methadone and referral to a detoxification center. If the patient accepts, he will then be taken to a detox center to start HCV therapy and where he will stay for an average of six months. If the patient does not accept referral to a detox center, the mobile harm reduction unit will administer therapy (directly observed therapy) to him and will be in charge off his follow up in the shantytown.

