2.6 Study Duration

2.7 Statistical Analysis and Sample Size Justification

PHASE I

Once all subjects have been included, the results from the Whatman 903 cards will be compared with those obtained by venipuncture at HUIL. Diagnostic performance will be assessed by calculating the area under the ROC curve (AUROC) for each virus. The Se, Sp, PPV, and NPV for each virus will also be calculated.

PHASE II

Sample size: Assuming that around 10,000 people visit Cañada Real Galiana on different days, a sample size of 930 randomly selected subjects will suffice to estimate, with a 95% confidence interval and a precision of ± 3 percentage points, a

population percentage considered to be around 60%. A replacement rate of 0% has been anticipated.

PHASE III

In order to evaluate the effectiveness of the intervention, the accuracy of HCV tests will be calculated at the population level (AUROC, Se, Sp, PPV, and NPV), as will the percentage of patients arriving at the clinic, the percentage of patients treated, and the percentage of patients cured of hepatitis C. The incidence of HCV reinfection will be assessed using a Kaplan-Meier survival method. In addition, the effectiveness of the intervention for HIV, HBV, and HDV infection will be evaluated.

Statistical Methods

The statistical analysis will be performed using IBM SPSS Statistics for Windows, Version 22.0 (IBM Corp, Armonk, New York, USA) and the R statistical package, version 3.2.2 (GNU General Public License). All tests will be two-tailed, with p-values of <0.05 considered statistically significant.

An assessment will be performed to determine the percentage of patients who are positive at screening, are referred to a health center, have their diagnoses confirmed, and are treated at the end of the study. Factors associated with virus transmission, lack of referral to a health center, and HCV treatment will also be analyzed.

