Continuous variables will be presented as mean and standard deviation; categorical data will be presented as absolute numbers and percentages. The prevalence (95% confidence interval) of antibody for HCV, HIV, and HDV, HBsAg, and active HCV infection will be calculated in the sample and in the subgroups studied. Categorical data and proportions will be analyzed using the chi-square test or Fisher exact test, as required. The *t* test, ANOVA, or Mann-Whitney test will be used to compare continuous variables. The association study will be performed using logistic regression and adjusting for the major epidemiological and clinical covariates.

VARIABLES INCLUDED

PHASE I: VARIABLES TO BE RECORDED DURING INTERNAL VALIDATION TESTING

- Date of birth
- Gender
- Date of sample collection
- Date of last analysis
- HCV antibody result from last analysis (positive/negative)
- HCV-RNA result from last analysis
- Genotype result from last analysis
- HIV antibody result from last analysis (positive/negative)
- CD4+ lymphocyte count for HIV-positive patients
- RNA-HIV result for HIV-positive patients
- HDV antibody result from last analysis (positive/negative)
- HBsAg result from last analysis (positive/negative)
- DNA-HBV result from last analysis
- Incidents or errors in sample collection (yes/no)

PHASE II: VARIABLES TO BE RECORDED DURING SCREENING

- Code allocated
- Date of sample
- Date of birth
- Gender (male/female)
- Nationality
- Homeless (yes/no)
- No. of days per week that the individual visits Cañada Real Galiana
- Drugs consumed (mark as relevant):
 - Heroin
 - Cocaine
 - Marihuana
 - Alcohol
 - Benzodiazepines
- Current use of parenteral methods (yes/no)
- Date when parenteral methods were first used
- Frequency of injections (daily [No. of times]/weekly [No. of times])
- Syringe sharing for >3 months (yes/no)
- Frequency of syringe sharing (daily/weekly/monthly)
- Date of switch from parenteral methods to smoking
- On methadone program (yes/no)
- Being monitored for HCV infection (yes/no)
- Have you previously been offered the chance to undergo HIV and/or HCV testing?
 - No
 - Yes, but I did not accept
 - Yes, with (positive/negative) results for HIV and (positive/negative) results for HCV
- Contact with health center (never, occasionally, regular monitoring).
 - Primary health care
 - Hospital
 - Drug abuse center
 - Other
- Advantages of alternative screening
- Drawbacks of alternative screening
- Contact data provided (yes/no)

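### The written plan does not provide for counting people who decline the screening test, so uptake cannot be reported and prevalence cannot be checked for refusal bias.

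*Combined protocol and SAP*

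**What the plan says.** Section 2.3, Phase II, describes an active search in the shantytown, with the test offered whether or not the person already knows their status. Selection is called both random and consecutive. Those who agree sign consent and give contact, social, demographic and drug-use data. For everyone, the text adds: "Regardless of whether or not individuals agree to take part in the study, they will all be given a card". This is the prevention and contact card, not the Whatman sampling card. No step is described that records a person who declines.

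The same section then states: "Data will be recorded on social and demographic details, the consumption habits of each PWID, and the acceptability of the screening test". Acceptability is not defined there, and no denominator is given.

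The Phase II variable list in section 2.7 opens with an allocated code and a sample date. Its nearest items to acceptability are the perceived advantages and "Drawbacks of alternative screening". Its one refusal item concerns earlier offers of HIV or HCV testing, not this one.

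The analysis text in section 2.7 begins its cascade with the percentage positive at screening and plans neither an uptake proportion nor a non-response analysis. The sample size rests on "a sample size of 930 randomly selected subjects will suffice to estimate" a "population percentage considered to be around 60" per cent, "with a 95% confidence interval and a precision of ± 3 percentage points", with a replacement rate of zero.

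The limitations in section 2.3 foresee refusal of referral. They do not mention bias from refusal of screening.

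**The concern.** The case for the finger-prick method in section 2.2 is partly that people will agree to it: "This method is more widely accepted than venous extraction". The closest this study can come to testing that in its own setting is the proportion of people approached who accept. That needs a count of those who decline. Opinions on advantages and drawbacks do not supply it.

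Prevalence has the same gap. Estimating it is secondary objective 4 and drives the 930. People who already know their status are also approached, so refusal could plausibly depend on infection. Some known positives may see no reason to be tested again; others may accept in the hope of treatment. The direction is therefore unknown.

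Objective 6 estimates prevalence again at 24 months. If uptake differs between the two rounds, a change in who accepts could look like a change in prevalence, or hide one.

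A refusal that was not recorded at the approach cannot be recovered at analysis.

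**Working it through.** **1. The plan's own sample size.** Inputs from section 2.7: p = 0.60, d = 0.03, 95% confidence (z = 1.96), and N = 10,000 from "Assuming that around 10,000 people visit Cañada Real Galiana on different days".

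- n0 = z²p(1 − p)/d² = 1.96² × 0.60 × 0.40 / 0.03² = 1,024.4
- With finite population correction: n = 1,024.4 / (1 + 1,023.4/10,000) = 929.3, rounded up to 930

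The stated figure reproduces exactly. Its half-width is ±3.00 points with the correction and ±3.15 without. Both describe sampling error only.

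**2. Bias from refusal.** Let u be uptake and g the difference in prevalence between accepters and refusers, in points.

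- Prevalence among all approached = u × (accepters) + (1 − u) × (refusers)
- Bias of the accepters' estimate = (1 − u) × g
- Gap at which bias equals 3 points: g = 3/(1 − u)

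The documents give neither u nor g, so the rows below are a range of assumptions. The bounds assume 60% prevalence in accepters and let refusers be anywhere from 0% to 100% infected: lower = 0.60u, upper = 0.60u + (1 − u).

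| Uptake (assumed) | Gap giving 3 points of bias | Bias at a 20-point gap | Worst-case bounds | People approached for 930 |
|---|---|---|---|---|
| 95% | 60 | 1.0 | 57–62% | 979 |
| 90% | 30 | 2.0 | 54–64% | 1,034 |
| 80% | 15 | 4.0 | 48–68% | 1,163 |
| 70% | 10 | 6.0 | 42–72% | 1,329 |
| 50% | 6 | 10.0 | 30–80% | 1,860 |

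At a 20-point gap, bias exceeds 3 points only when 1 − u > 3/20, that is, when uptake is below 85%.

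**3. Effect on the interval.** With n = 930, the nominal 95% interval covers the true value about 50% of the time if bias is 3 points and about 26% if it is 4 points.

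**4. The 24-month comparison (illustration).** Take a fixed 15-point gap, with uptake of 90% in one round and 70% in the other. The biases are 0.10 × 15 = 1.5 and 0.30 × 15 = 4.5 points. The apparent change is 3.0 points with no change in true prevalence.

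**5. What a count would give.** If 930 accept, uptake would be estimated to about ±1.8 points at 90%, ±2.3 at 80% and ±2.5 at 70%.

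**The case against.** The strongest reply is that this argues from silence. Section 2.3 promises acceptability data without limiting them to consenting participants, and Figure 2.4.2, the flowchart for this step, is not visible in the text reviewed. A reader might infer that refusers will certainly go uncounted. The documents do not establish that, only that the readable text makes no provision for counting them. Even if the figure has a refusal box, the variable list and the analysis text would still need the matching item.

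A reader might also infer that the acceptability data must come out favourable. That goes too far: the list asks about drawbacks, so people who accepted can still be critical. The fair point is narrower, that opinions are not uptake.

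Neither uptake nor acceptability is a listed objective in section 2.1, and prevalence is secondary. This limits the weight of the point, but prevalence is the quantity for which Phase II was sized.

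Finally, the limitations expect a significant share of people to consent. If uptake is very high the bias is small, as the 95% row shows. That is true, but only a count of people approached could demonstrate it.

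**Conclusion.** The point holds as a gap in what the written plan captures. Uptake has no denominator, and neither the prevalence estimate nor its 24-month repeat can be checked for refusal bias.

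The size is conditional. Bias passes 3 points only if the accepter–refuser gap exceeds 30 points at 90% uptake, 15 at 80% or 10 at 70%. At 95% it would need more than 60 points, which is very unlikely. These uptakes and gaps are assumptions, since the documents supply neither.

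Two stronger readings are not supported. One is that the prevalence estimate will be off by more than its stated precision: nothing in the documents fixes either the amount of refusal or how refusers differ. The other is that 930 is wrong because it allows nothing for refusal. The figure is correct on its own inputs as the number to be tested; refusal changes how many must be approached and what the ±3 leaves out.

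The change should be made before screening starts, because it is cheap and the information cannot be retrieved afterwards.

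**What to change.** - **Record.** Add an anonymous accepted/refused tally to the Phase II data form, completed when the information card is handed over. Include date, observed sex, approximate age and a mark for a repeat approach. The repeat mark matters because the variable list itself expects people to visit on several days a week.
- **Optional items.** Record known HCV status, injecting and reason for refusal only if volunteered and permitted by the ethics committee, because these people have not consented.
- **Define.** State that acceptability includes uptake: the number accepting divided by the number approached.
- **Report.** Give uptake with a 95% CI, separately for the first screening and the 24-month round.
- **Sensitivity analysis.** Bound prevalence over all people approached under stated assumptions for refusers, including the worst case (for example, with 60% in accepters, 54–64% at 90% uptake and 42–72% at 70%). Weighting on sex and age alone would not remove bias that arises because refusal depends on known infection, so the bounds should carry the argument.

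The 930 is unchanged. Section 2.3 already has a nurse, generally with an educator, giving something to every person and entering data on a mobile device. The cost is a few seconds per approach, a short added analysis and possibly a clarification with the ethics committee. Two limits remain: if repeats are missed, uptake is per approach rather than per person; and with no venepuncture arm, the count gives an uptake rate, not a comparison with venous sampling.

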PWID are at high risk from blood-borne infections, including human immunodeficiency virus (HIV) and HCV through the sharing of needles and injection equipment. Harm reduction refers to policies, programs and practices that aim to reduce the harms associated with the use of drugs in people unable or unwilling to stop. Harm reduction began to be discussed frequently after the threat of HIV spreading among and from PWID was first recognized. However, similar approaches have long been used in many other contexts for a wide range of drugs. There is persuasive evidence from the literature that harm reduction approaches greatly reduce morbidity and mortality associated with drug use and combined prevention measures (Needle and syringe programmes & opioid substitution therapy) contribute to the reduction of the spread of

HIV and HCV infections. Although there is concern that HCV re-infection may negate the potential benefits of treatment, the reported rates of reinfection following successful HCV treatment among PWID are low, especially when combining high coverage of harm reduction measures.

Cañada Real is a major shantytown on the outskirts of the city of Madrid. It is estimated that 90% of the illegal drugs in the Madrid region are sold and consumed in Sector VI of Cañada Real and that between 4000 and 6000 people per day go to this shantytown for their drug doses. The Anti-Drug Agency (Agencia Antidroga) runs a daily mobile unit in the area as a harm reduction strategy. The remit of the unit is to minimize damage from drug consumption by taking health-related, psychological, and social measures. It deals mainly with outreach drug consumers (individuals who are outside the reach of the health system and have great difficulty accessing it). This harm reduction unit identifies drug users at risk, offering them needles, syringes, opioid substitution therapy and screening for HIV and HCV. When a PWID tests positive for HIV or HCV, he is referred to Infanta Leonor Hospital for appropriate therapy. The harm reduction team accompanies the drug user to hospital and ensures his follow-up and adherence to therapy. Recent hepatitis C test and care programs have identified the use of patient navigators or care coordinators to be an important intervention in overcoming challenges to linkage to and retention in care

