Hepatitis C therapy will be prescribed according to European and regional guidelines. Current guidelines recommend treating PWID independently of the liver fibrosis stage. In this project, antiviral therapy will be chosen regarding interactions with other drugs or methadone and a once-daily therapy is preferred in those patients who decline being referred to a detox centre.

After HCV therapy has been completed, all PWID will be periodically screened for hepatitis C (analyzing RNA HCV) to detect infection. Depending on the drug users risk factors, screening for reinfection of HCV will be carried out on a 3 to 6 months schedule.

Infanta Leonor Hospital (HUIL) is the reference specialized health centre for Cañada Real shantytown. All PWID diagnosed of HIV and HCV in this shantytown are referred to the HUIL internal medicine department for evaluation. The hospital is highly coordinated with the harm reduction unit. Nurses or doctors from the harm reduction unit accompany the patients to the specialized clinic.

ETHICAL ISSUES

All patients will sign an informed consent form. Confidentiality will be maintained with regard to personal and genetic data in accordance with the basic ethical principles for research involving biological samples and the provisions of applicable legislation (Organic Law 15/1999 of 13 December on Data Protection, Law 41/2002 on Patient and Healthcare Autonomy and Law 14/1986 on General Health). The ethical research principles set out in the Declaration of Helsinki and the Belmont Report will be adhered to, as will those of the UNESCO Universal Declaration on the Human Genome and Human Rights. The requirements of Spanish legislation on processing on personal data will also be met. The research project has been approved by the Research Committee at HUIL and the Ethics Committee of Hospital General Universitario Gregorio Marañón and ISCIII.

LIMITATIONS OF THE STUDY

The study may be limited by the possibility of not reaching the required number of subjects, although we believe this to be unlikely given the large number of people who visit Cañada Real Galiana. Furthermore, the limit of HCV detection by real-time PCR is approximately 1000 IU/mL, although we believe that with this limit we may detect the vast majority of active infections, since HCV viral load in untreated patients tends to be greater than 1000 IU/mL. Moreover, previous publications show 94% sensitivity and specificity for the Whatman card.

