In contrast with the rapid tests, sample processing is centralized, so results are not available immediately. Given that screening is performed in an unfavorable setting and on an outpatient basis, a series of problems could arise, as follows: (1) errors in the processing of samples (eg, insufficient sample volume contamination, loss); (2) difficulties in contacting participants once the results are available; and (3) the assumption that although a significant percentage of consumers will consent to screening, many will refuse referral to a health center for confirmation of diagnosis and treatment.

GENERAL TASKS

1. Administrative tasks: Classification by the Spanish Agency for Medicines and Medical Devices (AEMPS) and presentation to the Clinical Research Ethics Committee (CEIC).
2. Contracting of IT services. Design of online data collection forms.
3. Final design of protocol and informed consent forms.
4. Design of database and adaptation of online data collection forms.
5. Initial meeting of researchers.
6. Six-monthly teleconferences for researchers.
7. Phase 1: Recruitment, collection of informed consent forms, collection of

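### Reinfection is seen only at RNA tests whose spacing depends on risk, so an ordinary Kaplan-Meier curve partly reflects the testing schedule

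*Combined protocol and SAP*

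**What the plan says.** Section 2.3 (Phase III) states that after therapy "all PWID will be periodically screened for hepatitis C (analyzing RNA HCV) to detect infection", and adds: "Depending on the drug users risk factors, screening for reinfection of HCV will be carried out on a 3 to 6 months schedule". Section 2.7 (Phase III) gives the whole analysis in one sentence: "The incidence of HCV reinfection will be assessed using a Kaplan-Meier survival method".

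The text does not give a definition of the reinfection event, a time origin, an event date, a censoring rule or the specimen (card or venous blood). The Phase III variable list in section 2.7 ends with virological response 12 weeks after therapy. It has no field for the dates or results of later RNA tests, and loss to follow-up is a yes/no item without a date.

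Confirmation is described for the Cañada Real screen. A positive person is offered referral "to confirm the result and assess whether monitoring should begin" (section 2.3, Phase II), and of the first hospital visit the plan says: "These blood tests will confirm the results from the screening for HCV in Cañada Real" (Phase III).

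The only accuracy figure is in the limitations paragraph of section 2.3: "previous publications show 94% sensitivity and specificity for the Whatman card".

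**The concern.** Kaplan-Meier assumes that the event time is known, or that the person was known to be event-free at censoring. Here reinfection is silent between tests. With no dating rule, the natural use of the method puts the event on the day of the positive test. The average delay is then about half the testing interval: 1.5 months on a 3-month schedule and 3 months on a 6-month schedule. Because risk factors set the schedule, the delay differs systematically between higher-risk and lower-risk people.

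This matters because section 2.2 raises reinfection as the worry that could cancel the benefit of treatment, and answers that "the reported rates of reinfection following successful HCV treatment among PWID are low". When few events are expected, small shifts in timing or a few spurious positives change the estimate noticeably. A difference between risk groups could not be separated cleanly from the difference in how often they were tested.

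**Working it through.** **The plan's own figure.** There is none for reinfection: no expected rate, event count or sample size. The only sample size (930) is for Phase II prevalence and has no bearing here.

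**Inputs.** Tests every 3 or every 6 months (section 2.3). Constant true reinfection rate of 2, 5 or 10 per 100 person-years; these are assumptions, since the documents say only that reported rates are low. Events dated at the positive test; also an assumption, since no rule is given.

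**Step 1: dating, perfect test.** The curve at time t shows only infections acquired up to the last scheduled test, so F(t) = 1 − exp(−rate × time of last test in years). At month 9 the last test is at month 9 (0.75 years) on the 3-month schedule and at month 6 (0.5 years) on the 6-month schedule.

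- Rate 0.05: 1 − exp(−0.0375) = 3.7% vs 1 − exp(−0.025) = 2.5%.
- Rate 0.02: 1 − exp(−0.015) = 1.5% vs 1 − exp(−0.01) = 1.0%.
- Rate 0.10: 1 − exp(−0.075) = 7.2% vs 1 − exp(−0.05) = 4.9%.

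At month 12 both schedules have just tested. At rate 0.05 both read 1 − exp(−0.05) = 4.9%. With an assumed sensitivity of 94% they read 4.8% vs 4.7%. The gap therefore opens between shared visits and closes at them.

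**Step 2: pooled curve.** With half the people on each schedule and rate 0.05, the pooled curve at month 9 reads (3.7% + 2.5%)/2 = 3.1%, against a true 3.7%.

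**Step 3: censoring.** Take a person last tested (negative) at month 6 and last contacted at month 11. Censoring at last contact counts 11 − 6 = 5 untested months as event-free. Censoring at the last negative test does not.

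**Step 4: false positives, only if a single positive counts.** With nobody truly reinfected and independent errors, the probability of at least one false positive in k tests is 1 − Sp^k. Over 12 months k = 4 (3-monthly) or k = 2 (6-monthly).

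- Sp 99.9%: 1 − 0.999^4 = 0.4% vs 1 − 0.999^2 = 0.2%.
- Sp 99%: 1 − 0.99^4 = 3.9% vs 1 − 0.99^2 = 2.0%.
- Sp 94%, worst case: 1 − 0.94^4 = 21.9% vs 1 − 0.94^2 = 11.6%.

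The ratio is about 2 throughout, but the absolute size runs from negligible to dominant. If a second, independent positive is required, 1 − Sp is replaced by (1 − Sp)². The results become 1.4% vs 0.7% at 94%, and 0.04% vs 0.02% at 99%. Errors that recur in the same person would accumulate more slowly, and a second sample would remove fewer of them.

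**The case against.** A reader might infer that the reinfection estimate will be mainly false positives. The documents do not support that:

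- The 94% is a literature figure for the card, with no analyte named. Card screening begins with antibody ELISA, whereas reinfection testing is by RNA.
- Card use after therapy is itself an inference, from the harm reduction unit following in the shantytown those who decline the detox center. The task list points the other way: post-therapy follow-up is assigned to the hospital and the harm reduction unit, not to the laboratory that processes the cards.
- A confirmation route exists, since people diagnosed in the shantytown are referred to the hospital. The flow charts are not reproduced in the text available, so they cannot be checked for a further step. What is missing from the text is an endpoint rule, not a care pathway.

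These points stand, and they make the false-positive part conditional.

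It can also be said that the dating effect is small, that reinfection is not among the seven listed objectives, and that no comparison of reinfection by risk group or testing interval is planned. That too is fair, and it limits the weight of the point. But step 2 shows that the pooled curve is also affected. Treatment starts at different times within a 24-month study, so follow-up will be short and uneven, and curves are likely to be read between shared visits.

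**Conclusion.** The point holds in a limited form. Reinfection times are interval-censored with widths that depend on risk, and ordinary Kaplan-Meier with detection dating suits such data poorly. At an assumed 5 per 100 person-years with a perfect test, equal true incidence appears as about 3.7% vs 2.5% at month 9 and is nearly equal at month 12. This part needs no assumption about specificity. It rests on the two fixed intervals, a constant rate and dating at the positive test.

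The accumulation of false positives is a conditional addition. It applies if single card-based RNA positives are counted, and its size (0.4% vs 0.2% up to a worst-case 21.9% vs 11.6% at 12 months) depends on a specificity that the documents do not give. With hospital venous RNA it largely disappears and the dating effect remains.

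**What to change.** In section 2.7, and without touching the clinical testing schedule:

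- Add to the Phase III variables the date, specimen and result of each post-therapy RNA test.
- State the time origin and the event definition. Estimate incidence with an interval-censored method such as Turnbull's, or at least date each event at the midpoint between the last negative and first positive test.
- Censor at the last negative RNA test, not at last contact.
- Show results by testing interval.
- Report incidence twice: for reinfections confirmed by the hospital test that referred positives are already offered, and for all RNA positives. Both are needed because the limitations paragraph expects many to refuse referral. Leaving out unconfirmed positives could bias incidence downward.

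The cost is a few more data fields, a little more analysis work and a slightly less simple estimate. Midpoint dating removes the average lag but still moves in steps: 6-monthly infections from months 6 to 12 would all fall at month 9. The interval-censored estimate is therefore preferable, and either is best read at visits that the two schedules share.
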